In- and exclusion criteria for trial sites (practices)	
Inclusion criteria
 
 - General practice cares for patients covered by statutory health insurance and is active in primary care - Specialist doctor for general practice or internal medicine, or doctor with no specialist field. - Practice has internet access - Investigator's agreement to fulfil the contractual obligations arising from the trial - Investigator's agreement to the training of a HCA from the practice for the intervention, as required by the trial 
Exclusion criteria
 
 - Practice focuses on unconventional medical treatments - Practice focuses on special indications (e.g. HIV)
In- and exclusion criteria for patients	
Inclusion criteria:
 
 - Age ≥ 60 and - ≥ 3 chronic diseases affecting ≥ 2 organ systems, requiring pharmaceutical treatment and - ≥ 5 long-term prescriptions with systemic effects and - Health care provided by GP (at least one contact in most recent quarter) and - Patient is legally competent to sign any documents and - Ability to understand and participate in trial of own free will, to fill out questionnaires and participate in telephone interviews as well as - Written informed consent to participate in trial 
Exclusion criteria:
 
 - Diseases cause life expectancy of < 12 months - Abuse of alcohol or illegal drugs and visible clinical signs or symptoms thereof - Cognitive disability that prevents trial participation (MMSE < 26) - emotional stress that prevents participation in trial - Participation in a clinical investigation within the last 30 days
Outcomes	
Primary outcome: difference in Medication Appropriateness Index (MAI)-Score 6 months from baseline minus baseline (MAI T1–T0)
 
Secondary outcomes: MAI T2-T0 and the difference in the following scores 6 and 9 months from baseline minus baseline (T1-T0 and T2-T0): EQ-5D, VES-13, all cause hospitalisation, medication adherence (observed: AS, DS, DoS, RS, self-reported: Morisky-Score), MRCI, BMQ, pain assessment (grade of severity of chronic pain in accordance with M. von Korff, J. Ormel et al. 1992), satisfaction with shared decision making (MSH), patient's future expectation, expected / desired lifetime duration, cognitive dysfunction (VFT), depression (GDS)

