Multiple disorders in patients are likely to result in multiple drug prescribing but may also result in under-treatment, in particular in the elderly: too little prescriptions or too low dosages have been reported in patients with multimorbidity/polypharmacy, asking for additional prescription(s).⁶⁻¹⁰ The potential risks and harmful consequences of polypharmacy, such as drug-drug and drug-disease interactions which potentially cause adverse drug events (ADE), as well as the decreased adherence of patients to complex regimens of multiple medications, are research objectives in pharmacology and geriatrics.¹¹⁻¹³ Several studies investigated inappropriate prescribing and potentially preventable ADE.¹⁴⁻¹⁶ In consequence, guidance on rational prescribing in multimorbid patients recommend a prudent, drug-sparing, and patient centred, not disease-oriented approach: clear therapeutic objectives, prioritisation according to the severity of diseases, efficacy and safety of available therapies, therapeutic individualisation and monitoring, patient implication and attention to their desires and expectations, and avoiding under-treatment.^{1,11-13,17,18} Nevertheless, the implementation of these recommendations is still insufficient, as ongoing studies on the prevalence of inappropriate prescribing demonstrate. In our cross-sectional study in 18 general practices and 169 elderly multimorbid adults, patients received a median of 8 drug prescriptions (range 5-16).¹⁹ We found non-considerations of drug-disease interactions in 15%, the necessity of renal dose adjustments in 23%, drug-drug interactions in 25% and an inappropriate choice and dosage of medicines with regard to age in 21% of the patients.²⁰ Major issues are the often lacking therapeutic goals and their prioritisation as well as inadequate communication with patients.^{21,22}

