5.2.3 Patient criteria

Inclusion criteria:

- At least 60 years of age
- Multimorbidity, defined as the existence of at least three chronic diseases, which:
 - o Affect at least two different organ systems
 - o Require pharmaceutical treatment
 - o Represent a disease entity, i.e. arthritis affecting different joints (arthritis of the knee, arthritis of the hip, etc.) is counted as one disease “polyarthritis”, irrespective of the location
 - o Are not coded in the International Classification of Diseases, version 10 (ICD-10, 2010) in the chapter “H” (diseases of the eye and adnexa, or of the ear and mastoid process) or in the chapters “E00” to “E04” (diseases of the thyroid gland: congenital iodine-deficiency syndrome, iodine-deficiency-related thyroid disorders and allied conditions, subclinical iodine-deficiency hypothyroidism, other hypothyroidism and other non-toxic goitre), since the latter require substitution of iodine and/or thyroxine, only.
- Multimедication, defined as follows: Regularly takes at least five medicines (long-term medication) with systemic effects.
- Care is provided by a GP working at a trial site (at least one contact in most recent quarter).
- Patient is legally competent to sign any documents,
- Patient is capable to give a free and written informed consent to participate in the trial, to fill in questionnaires and to participate in telephone interviews.

Exclusion criteria:

- Diseases that result in an estimated patient’s life expectancy under 12 months
- Alcohol or illegal drug abuse with recognisable clinical signs or symptoms
- Cognitive impairment (MMSE < 26), that would prevent participation in the trial
- Emotional stress that would prevent participation in the trial
- Participation in a clinical trial within the last 30 days.

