- Discrepancy score, DS (Sum of all differences in drug, time of intake, frequency and dose) / Sum of all prescriptions, $AS < 0.8$ or $> 0.2 = 1$
- Drug Score (DS, Sum of all drugs taken/sum of all prescriptions), $DS < 0.8$ or $DS > 1.2 = 1$ ⁴⁶
- Dose Score, (DoS, Sum of all daily doses taken/sum of all prescriptions), $DoS < 0.8$ or $DoS > 1.2 = 1$ ⁴⁶
- Regimen Score (RS, actual frequency of intake per day / prescribed frequency per day), $RS < 0.8$ or $DS > 1. = 1$ ⁴⁶
- Change in self-reported adherence measured as the difference in the Morisky-Score⁴⁷ 6 months from baseline minus baseline (T1–T0) and 9 months from baseline minus baseline (T2–T0)

5) Change in perceived future life expectancy reflects concepts of will to life or years of desired life [YDL] measured as the difference of the three items future expectation / expected lifetime duration / desired lifetime duration in the interval 6 months from baseline minus baseline (T1–T0) and 9 months from baseline minus baseline (T2–T0): Desired and expected life time duration are considered to be sensitive for personal experiences and scientific influences,⁴⁸ as well as indicating well being and positive life evaluation.⁴⁹ Moreover it is argued that YDL itself reflects mortality on the long run. Thus, if our intervention effects change in YDL, one might argue that participants consider the intervention as relevant in relation to their own life expectancy and life quality.

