15 APPENDIX A

15.1 Abbreviations

ADR	Adverse Drug Reaction
AMG	Medication law
AS	Discrepancy score
BMQ	Beliefs about Medicines Questionnaire
CDSS	Computerized Decision Support System
CIRS	Cumulative Illness Rating Scale
CR	Center registration
CRF	Case Report Form
DEGAM	German Society of General Practice and Family Medicine
DS	Drug Score
DoS	Dose Score
GCP	Good Clinical Practice
GDS	Geriatric Depression Scale
GP	General Practitioner
HCA	Health Care Assistant
ICC	Intra-Cluster Correlation-coefficient
ICH	International Conference on Harmonisation
ID	Identifier
IGP	Institute for General Practice, Goethe university Frankfurt, Coordinating centre of the study
ITT	Intention To Treat
MAI	Medication Appropriateness Index
MSH	Man-Son-Hing scale
MediMoL	Medication Monitoring List
MMSE	Mini Mental Status Exam
MRCI	Medication Regimen Complexity Index
OTC	Over The Counter
PP	Per Protocol
PZN	National Drug Code
RS	Regimen Score

SOP	Standard Operating Procedure
SPSS	Statistical Package for Social Sciences (Software)
TMF	Trial Master File
VES-13	Vulnerable Elderly Survey, 13 items
VFT	Verbal Fluency Test
VRS	Verbal Rating Scale on pain

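### The upper limit of the Regimen Score's non-adherence rule names DS instead of RS and prints an incomplete cut-off

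*Protocol*

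**What the plan says.** The synopsis (section 1.4) lists among the secondary outcomes "medication adherence (observed: AS, DS, DoS, RS, self-reported: Morisky-Score"). Section 8.1.2, item (5), gives the scoring rules, in which 1 marks a value outside the tolerated range:

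- Drug Score: "Drug Score (DS, Sum of all drugs taken/sum of all prescriptions), $DS < 0.8$ or $DS > 1.2 = 1".
- Dose Score: "Dose Score, (DoS, Sum of all daily doses taken/sum of all prescriptions), $DoS < 0.8$ or $DoS > 1.2 = 1".
- Regimen Score: "Regimen Score (RS, actual frequency of intake per day / prescribed frequency per day), $RS < 0.8$ or $DS > 1. = 1".

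The same list introduces a fourth score as "Discrepancy score, DS (Sum of all differences in drug, time of intake, frequency and dose) / Sum of all prescriptions". It is labelled DS there, but its own cut-off is written with AS. The abbreviation list (section 15.1) assigns AS to "Discrepancy score" and DS to the Drug Score. The RS cut-off is not restated anywhere else in the protocol.

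**The concern.** RS compares actual with prescribed frequency of intake, so both limits of its flag should be limits on that ratio. Only the lower one is. The upper one refers to a different score, and the number it uses is visibly unfinished.

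If the rule is programmed as printed, the Regimen Score flag cannot respond to a frequency that is too high, and it can be set by the number of drugs taken when every prescribed frequency is followed. That matters here because the intervention (Appendix B) includes a review of everything the patient takes. It could change the number of drugs taken in one arm, and so move the RS flag, with no change in how often drugs are taken. Medication adherence is a named secondary objective (section 3), so a mislabelled regimen effect could reach the report.

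**Working it through.** No sample size, power or alpha figure depends on this rule, so there is no planned figure to reproduce. The check applies the printed rule to simple cases.

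**Inputs.** The definitions of RS, DS and DoS come from section 8.1.2. DS is read as the Drug Score, following section 15.1. DoS is read as daily dose taken over daily dose prescribed. The number of prescriptions n runs from 5 to 16: the inclusion criterion in section 5.2.3 is "Regularly takes at least five medicines (long-term medication) with systemic effects", and section 2.1 reports from an earlier cross-sectional study that "patients received a median of 8 drug prescriptions (range 5-16"). The printed upper cut-off is tried as 1.0 and as 1.2.

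**Step 1: intake too frequent, all prescribed drugs taken and none added.** DS = n/n = 1, which exceeds neither 1.0 nor 1.2.

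| RS | Printed rule | Upper limb RS > 1.2 (assumed) |
|---|---|---|
| 1.25 | 0 | 1 |
| 1.5 | 0 | 1 |
| 2 | 0 | 1 |
| 3 | 0 | 1 |

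The printed rule gives 0 in every row under either value of the cut-off.

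**Step 2: do the other scores see these patients?**

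- Dose per intake unchanged: DoS = RS = 1.25 to 3, above 1.2, so the Dose Score flags all four.
- Same daily dose split into twice as many intakes: RS = 2/1 = 2, DoS = 1/1 = 1 and DS = 1. The Drug, Dose and Regimen flags are all 0.

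**Step 3: every prescribed frequency followed (RS = 1), extra drugs taken, none omitted.** DS = (n + k)/n for k extra drugs.

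| n | DS, one extra | > 1.0 | > 1.2 | DS, two extra | > 1.2 |
|---|---|---|---|---|---|
| 5 | 6/5 = 1.200 | yes | no | 7/5 = 1.400 | yes |
| 8 | 9/8 = 1.125 | yes | no | 10/8 = 1.250 | yes |
| 9 | 10/9 = 1.111 | yes | no | 11/9 = 1.222 | yes |
| 10 | 11/10 = 1.100 | yes | no | 12/10 = 1.200 | no |
| 16 | 17/16 = 1.063 | yes | no | 18/16 = 1.125 | no |

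In general, (n + 1)/n > 1.2 requires n < 5, and (n + 2)/n > 1.2 requires n < 10.

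- Cut-off 1.0: one extra drug sets the Regimen Score to 1 at every n, although RS = 1 and the Drug Score (limit 1.2) codes the same patient 0.
- Cut-off 1.2: one extra drug is never enough. Two are enough for n = 5 to 9, which includes the median of 8. The upper limb is then identical to the Drug Score's own upper limb.

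**Step 4: one drug added and one omitted.** DS = n/n = 1, so the upper limb does not fire under either value.

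**The case against.** The best defence is that this is a typing slip which a careful programmer would correct. RS is defined in the same line, both neighbouring scores test their own ratio, and the lettering of the list is loose elsewhere. The protocol also leaves detailed methods to an SAP, and it does not say whether the 0/1 flag or the underlying ratio will be compared between arms. If only the ratio is analysed, the flag does no harm. All of this is fair and lowers the severity. It does not make the printed rule right, and nothing else in the protocol corrects it.

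Three stronger readings are tempting and are not supported:

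- **That too-frequent intake would go undetected in the trial.** This holds for the RS flag only. The Dose Score flags it when the dose per intake is unchanged, and the Discrepancy score counts frequency differences. The cover is incomplete, though: split doses escape the Dose Score, and the Discrepancy score's printed cut-off (below 0.8 or above 0.2) is met by every value, so its flag separates no one.
- **That anyone taking one extra drug is coded regimen non-adherent.** This needs the cut-off to be exactly 1.0 and no drug to be omitted. The missing digit may have been lost in reading the PDF, and at 1.2 no patient with five or more prescriptions is flagged for one extra drug.
- **That an over-the-counter product alone would set the flag.** The telephone interview records such products (section 11.3.7), but section 8.1.2 does not say whether they count in the Drug Score numerator.

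DS could also be read as the Discrepancy score, since the list uses that label once. Excess frequency would then enter only through a count mixed with drug, timing and dose differences, and the limb would still not test RS.

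**Conclusion.** The point holds as an error in a scoring rule. The upper limb names the wrong score and lacks a complete number, so the RS flag has no upper limit on intake frequency and depends on the number of drugs taken instead. That conclusion does not depend on what the unfinished number was meant to be; only the number of extra drugs needed to trigger the flag does (one at 1.0; two, for 5 to 9 prescriptions, at 1.2).

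It rests on three assumptions: DS means Drug Score as in the abbreviation list, the rule is programmed as printed, and the flag is analysed. The share of patients who would be miscoded cannot be estimated from the protocol.

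Section 12.2 treats only the primary analysis as confirmatory. RS is one of several adherence scores and has no bearing on the primary endpoint or the sample size. Severity is minor to moderate.

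**What to change.** Before the adherence scores are programmed:

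1. Rewrite the upper limb of the Regimen Score rule in terms of RS and print the full cut-off. By analogy with the Drug and Dose Scores this is presumably RS > 1.2. That value is an inference, so the sponsor should confirm it against the source the protocol cites for all three scores.
2. Use AS for the Discrepancy score and DS for the Drug Score throughout section 8.1.2, in line with section 15.1, and check the Discrepancy score's cut-off at the same time.
3. Carry the same wording into the SAP and compute the Regimen Score flag from the RS variable alone.

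The cost is a line or two of text. No new data are needed, and the design and primary analysis do not change.

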8.1.3 Secondary outcomes to explain the intervention mechanisms

1) Change in complexity of medication measured as the difference 6 months from baseline minus baseline (T1–T0) and 9 months from baseline minus baseline (T2–T0) in terms of

- Total number of prescriptions
- Number of single doses / day
- Medication Regimen Complexity Index (MRCI),⁵⁰

since a high complexity is associated with a reduced adherence.²⁴

2) Change in health and illness beliefs and attitudes measured as the difference in the Beliefs about Medicines Questionnaire (BMQ) score²⁷ 6 months from baseline minus baseline (T1–T0) and 9 months from baseline minus baseline (T2–T0), since denial of illness and / or medication in general might explain non-adherence.²⁴

3) Change in severity of chronic pain measured as the difference in *Characteristic Pain Intensity score*, the *Disability Score*, in *Disability Points* and the resulting *Grades of chronic pain severity* in accordance with M. von Korff, J. Ormel⁵¹ et al. in the interval 6 months from baseline minus baseline (T1–T0) and 9 months from baseline minus baseline (T2–T0):

Prevalence of chronic or persistent pain in elderly ranges between 25 and 50%. Nevertheless, under-assessment and under-treatment of pain is frequent in the elderly.⁵² Under-treatment is often associated with polypharmacy,⁹ and is not adequately captured by MAI

appraisal. Therefore, pain is hypothesised as a surrogate for under-treatment^a and will be assessed to reveal possible negative intervention effects (i.e. a reduction of polypharmacy at a cost of an impaired pain management). The different scores to grade the severity developed by von Korff, Ormel et al. have been modified for, integrated in the German pain inventory (Deutscher Schmerzfragebogen – questions 11 a-c, and 12 a-d) and validated in a German population.^{51,53,54}

4) Change in satisfaction with shared decision making measured as the difference in the *Man Son Hing* scale (MSH)^{28,29} interval 6 months from baseline minus baseline (T1–T0) and 9 months from baseline minus baseline (T2–T0): For an appropriate prescription in elderly multimorbid patients a patient centred rather than a disease centred approach is recommended. MSH scale measures the satisfaction with the shared decision making process. It was found feasible, showed high reliability and sensitivity of change and acceptable validity in the German “arriba”-study conducted in primary care practices.²⁸

8.2 Timing of outcome assessment

Study visits: at baseline (T0), 6 months (T1) and 9 months (T2) after baseline. Each time the HCA makes a practice appointment with the patient, and measures body height and weight. Patients fill out a questionnaire in the practice and reply it to the HCA in a closed envelope before leaving. HCA and GP fill out a paper based case report form (CRF). At the end of each visit the HCA sends a control sheet by telefax to the IGP to inform that the visit has taken place. The completed CRF and patient questionnaire are sent by mail to the IGP. Immediately after the receipt of the control sheet trained members of the study team conduct the telephone interview with the patient.

Table 1: Study visits

Month	Before trial begins	0 T0	6 (+/- 1) T1	9 (+/- 1) T2
Visits				
Trial measures for control and intervention group				
Documentation training, GP and HCA	•			
Profile of practices participating in trial	•			
Sociodemographics of GP				
Sociodemographics of HCA	•			
Identification of potentially eligible patients – screening lists	•			
Random lists	•			
Patient registration sheet (In- and exclusion criteria, reasons for non-participation of patients; for included patients with written informed	•			

^a Additional searches should reveal literature, where a direct association between polypharmacy and under-treatment of pain is shown (references are welcome). Otherwise we will get the prevalence of severe pain in our population at baseline.

Month	Before trial begins	0	6 (+/- 1)	9 (+/- 1)
Visits		T0	T1	T2
consent also: name, first name, telephone number, MMSE score)				
CRF, practice documentation				

 Detailed sociodemographics, patient incl. Disease Management Program (DMP) status 		•		

 Patient's current diagnoses 		•	•	•

 Patient's current medication 		•	•	•

 Height and weight of patient 		•	•	•

 Laboratory test results of patient, if available (serum electrolytes K, Na, serum creatinine) 		•	•	•

 Degree of patient's multimorbidity (CIRS) 		•	•	•

 Existing co- and multimorbidity of patient (Charlson Comorbidity Index) 		•	•	•

 Hospital stays (duration, reason) 		•	•	•

 Consultation of specialists 		•	•	•
Patient questionnaire:				

 Sociodemographics incl. best school leaving certificate and professional certificate, household composition, housing indicators, house care 		•		

 Lifestyle 		•		

 Generic health related quality of life (EuroQuoL, EQ-5D)) 		•	•	•

 Functional disability (Vulnerable Elderly Survey, VES-13) 		•	•	•

 Attitude of patients to medicinal therapy (Beliefs about Medicines Questionnaire, BMQ) 		•	•	•

 Severity of chronic pain in accordance with M. v. Korff, J. Ormel et al. 1992 		•	•	•

 Satisfaction with shared decision making (Man-Sin-Hong scale) 		•	•	•

 Future expectation, expected / desired lifetime duration 		•	•	•
Telephone interview with patient				

 Sociodemographics 		•		

 Current patient medication (incl. National drug code: PZN) 		•	•	•

 Symptoms for adverse drug reactions 		•	•	•

 Infirmity index (Sherbrooke Questionnaire) 		•	•	•

Month	Before trial begins	0	6 (+/- 1)	9 (+/- 1)
Visits		T0	T1	T2
• Depression (Geriatric Depression Scale, GDS)		•	•	•
• Cognitive dysfunction (Verbal Fluency Test)		•	•	•
• Self reported adherence of patient (Morisky)		•	•	•
Measures for intervention group only				
• Intervention: Training for GP's and HCA's		• [#]		

[#]After baseline completion

9 POST-RECRUITMENT RETENTION STRATEGIES

Co-ordinating Centre responsibilities of the IGP:

- Provide study materials incl. self-addressed envelopes which will be supplied to the trial sites in sufficient quantities and postage will be paid by the recipient
- Help ensure complete data collection at baseline, at six months and at nine months
- Respond to any questions (e.g. from practices) about the trial via telephone and telefax (regular office hours Mon. to Fri. 9:00 a.m. to 5:00 p.m.), or mobile phone (Mon. till Fri. between 9:00 a.m. and 7:00 p.m., Sat. & Sun. between 10:00 a.m. and 6:00 p.m.), or email

10 SAFETY MONITORING AND ADVERSE EVENTS

No safety monitoring nor adverse events reporting will be conducted, since worse treatment than previous to the trial is not possible. The study team of the trial (Institute for General Practice, Johann Wolfgang Goethe-University, Frankfurt am Main, IGP) has no influence on the diagnostic-therapeutic decision-making of the GPs and their patients.

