13.4 Finance and Insurance

No patient insurance is necessary for this trial, as it represents no health risk to patients.

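### Section 10 waives safety monitoring on a premise that section 8.1.3 contradicts, and deaths and reported adverse drug reaction symptoms have no planned comparison by arm

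*Protocol*

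**What the plan says.** Section 10 makes an explicit decision and gives its reason: there will be neither safety monitoring nor reporting of adverse events, because "worse treatment than previous to the trial is not possible". It adds that the study team "has no influence on the diagnostic-therapeutic decision-making of the GPs and their patients". Section 13.4 rests on the same view of risk, for insurance only: "No patient insurance is necessary for this trial, as it represents no health risk to patients".

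Section 8.1.3 takes a different view. It notes that under-treatment often accompanies polypharmacy and that the MAI does not capture it adequately. Pain therefore serves as a surrogate and "will be assessed to reveal possible negative intervention effects". The example it gives is fewer drugs at the price of poorer pain management.

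Table 1 in section 8.2 lists "Symptoms for adverse drug reactions" in the telephone interview at T0, T1 and T2 for both arms, and section 11.3.7 describes the same item. Section 11.8.2.2 asks for the date and circumstances of a death where possible. For patients who end participation early without withdrawing consent, it asks for survival status or a hospital stay at the end of the regular observation period.

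**The concern.** A protocol cannot hold that harm is impossible and also name a harm that it sets out to look for. The intervention is meant to change drug treatment: under section 2.3 the GP and the patient settle on a new medication after the CDSS check and the HCA interview. That the study team does not prescribe is true, but it does not show that the changed prescriptions carry no risk.

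At stake is what the trial can say about harm. If section 10 stands as the reason for not looking, the report could show better MAI scores and repeat that there was no risk, without setting deaths or ADR symptoms side by side by arm. ADR symptoms also matter for benefit: the synopsis lists avoiding adverse drug reactions among the desired effects, and section 2.3 holds out a possible reduction in them.

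**Working it through.** **Step 1: the premise.** The contradiction needs no arithmetic. Section 10 says treatment cannot become worse and section 13.4 says there is no health risk. Section 8.1.3 says a negative effect is possible and measures an outcome to detect it. These statements cannot all be right.

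**Step 2: which harm-related data have a planned comparison by arm?**

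| Item | Collected | Listed outcome? | Planned comparison by arm |
|---|---|---|---|
| Severity of chronic pain, including grades | Questionnaire at T0, T1, T2 | Yes (8.1.3) | Yes |
| All-cause hospital days | CRF at T0, T1, T2 | Yes (8.1.2) | Yes |
| ADR symptoms | Telephone interview at T0, T1, T2 | No | None stated |
| Deaths, survival status | On occurrence, or at end of observation (11.8.2.2) | No | None stated |

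The two entries of Yes in the last column follow from section 12.2: secondary endpoints use the multilevel approach of the primary analysis, in which treatment group is a fixed factor. The only outcome-related use stated for interview symptoms is as an input to the MAI rating (section 8.1.1). So two of four items are covered and two are not.

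**Step 3: does the hospitalisation comparison work as written?** Section 11.8.2.2 lists hospitalisation for any reason before T2 as a premature end of participation, while section 8.1.2 counts hospital days as an outcome. Section 12.2 plans a complete case analysis and, for losses to follow-up, the last available or baseline value carried forward. A patient admitted before T1 whose participation then ends is absent from a complete case analysis. If baseline is carried forward, the pain change is T0 − T0 = 0. The end-of-observation record in section 11.8.2.2 has no stated analysis. How many patients this would affect cannot be derived from the protocol.

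**Step 4: how precise would the added comparisons be?** Inputs from section 12.3: average cluster size 7, ICC 0.03, 31 practices per arm.

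- Design effect: 1 + (7 − 1) × 0.03 = 1.18, as stated.
- Patients per arm: 31 × 7 = 217, as stated. A noncentral t calculation with d = 0.3 and degrees of freedom based on practices gives power 0.795 with 30 practices per arm and 0.808 with 31, so the plan's number reproduces.
- Half-width of the 95% CI for a difference in proportions, with the same incidence p assumed in both arms: 1.96 × √(2 × p × (1 − p) × 1.18 / 217).

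| Assumed p | 2p(1 − p) × 1.18 / 217 | Half-width |
|---|---|---|
| 0.05 | 0.000517 | 4.5 points |
| 0.10 | 0.000979 | 6.1 points |
| 0.20 | 0.001740 | 8.2 points |

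The incidences are assumptions, since the protocol gives none. The ICC of 0.03 was assumed for change in MAI, not for events. The figures are illustrative only.

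**The case against.** The strongest objection is that the protocol already looks for the harm it names. A reader might infer from section 10 that the harm data would go unanalysed, or that MAI could improve while under-treatment worsened unseen. The document does not support either inference. Pain is measured for that very purpose, hospital days are a secondary outcome, and both are compared by arm with clustering taken into account. EQ-5D, VES-13 and GDS are further secondary outcomes in the synopsis that could show worsening health. Nor does section 13.4 cancel any reporting, since it concerns insurance alone. This part of the objection stands and confines the gap to ADR symptoms and deaths.

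It can also be said that tables of deaths and symptoms are ordinary SAP content, that the SAP is not at hand, and that section 10 waives monitoring and event reporting rather than description of data at the end of the study. That is partly right: the SAP may contain such tables, and nothing in the protocol forbids them. But it does not rescue section 10, which is an explicit decision resting on a reason the protocol itself contradicts. An SAP cannot correct that reason.

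Finally, ADR symptoms are not unused, because they inform the MAI rating. But serving as an input to a blinded appropriateness score is not a comparison of symptoms between arms.

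The precision figures do not measure the defect. They show only what the added tables could tell.

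**Conclusion.** The point holds in a limited form. The claim that treatment cannot become worse, and the related statement on insurance, conflict with section 8.1.3 and must be reconciled with it. Two of the four harm-related items collected in both arms, ADR symptoms and deaths or survival status, have no comparison by arm in the protocol. The hospitalisation outcome also sits badly with hospitalisation as a reason for ending participation.

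The primary analysis of change in MAI is not affected. What changes is the trial's ability to make a statement about harm. On the assumptions above, the data already planned would be informative for common symptoms. At an assumed 5% incidence the half-width of 4.5 points is almost as large as the incidence itself, so a comparison of deaths would be descriptive. The conclusion about the missing comparisons rests on the protocol alone, since the SAP was not available.

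**What to change.** 1. Remove from section 10 the claim that worse treatment cannot occur, and reconcile sections 10 and 13.4 with section 8.1.3. What monitoring or insurance should follow is for the sponsor and the ethics commission, and no rule is proposed here.
2. State that deaths and interview-reported ADR symptoms will be tabulated by arm, with differences and 95% confidence intervals that allow for clustering, and reported next to the planned pain and hospitalisation comparisons.
3. Reconcile section 11.8.2.2 with the hospitalisation outcome in section 8.1.2, and report the number of patients admitted per arm.

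The cost is protocol wording and one set of tables, with no new data collection. Section 13.1 lists a revised risk estimate for participants among the changes that need renewed ethics approval, so the rewording may have to be submitted. The statistical downside is that intervals for rare events such as death will be wide, and the report should say that a wide interval does not show absence of harm.
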